8.0 Hematologic Toxicities	
	Administer methylprednisolone 1 g IV daily for 3 days, with the first dose typically administered immediately after the first PEX May offer rituximab In case of management with rituximab, ICPi treatment will be discontinued
8.3 Hemolytic uremic syndrome	

Definition: A disorder characterized by a form of thrombotic microangiopathy with renal failure, hemolytic anemia, and severe thrombocytopenia. Signs and symptoms of hemolytic uremic syndrome can include:
 
Bloody diarrhea
 
Decreased urination or blood in the urine
 
Abdominal pain, vomiting, and occasionally fever
 
Pallor
 
Small, unexplained bruises or bleeding from the nose and mouth
 
Fatigue and irritability
 
Confusion or seizures
 
High blood pressure
 
Swelling of the face, hands, feet, or entire body
	

Diagnostic work-up
 
History and physical examination (special consideration for new history of high-risk drugs, hypertension, or cardiac causes)
 
CBC with indices
 
Blood smear morphology. Note that the presence of schistocytes on smear is critical for diagnosis.
 
Serum creatinine
 
ADAMTS13 (to rule out TTP)
 
Homocysteine/methylmalonic acid
 
Complement testing C3, C4, CH50 (complement inhibitory antibodies for suspected familial)
 
Evaluate reticulocyte count and mean corpuscular volume
 
Evaluation of infectious cause, including screening for EBV, CMV, HHV6
 
Evaluation for nutritional causes of macrocytosis (B12 and folate)
 
Pancreatic enzymes
 
Evaluation for diarrheal causes, shiga toxin, Escherichia coli 0157, etc
 
Direct antibody test (Coombs test), haptoglobin, LDH, and other etiologies of anemia
 
Evaluation for common drugs causing hemolysis (tacrolimus, cyclosporine, sirolimus, etc)
 
Evaluation for concurrent confusion
	
Grading	Management
G1-2: Evidence of RBC destruction (schistocytosis) without clinical consequences of anemia, thrombocytopenia Grade 2 G3: Laboratory findings with clinical consequences (eg, renal insufficiency, petechiae) G4: Life-threatening consequences (eg, CNS thrombosis/ embolism or renal failure)	For G1 and G2: Continue ICPi with close clinical follow-up and laboratory evaluation Supportive care For G3 and G4: Permanently discontinue ICPi Begin therapy with eculizumab therapy 900 mg weekly for four doses, 1,200 mg week 5, then 1,200 mg every 2 weeks Red blood transfusion according to existing guidelines
8.4 Aplastic anemia	

Definition: Condition in which the body stops producing enough new blood cells
 
Diagnostic work-up
	

8.0 Hematologic Toxicities	
History and physical examination (close attention to medications, exposure to radiation, toxins, recent viral infections) CBC, smear, reticulocyte count Viral studies, including CMV, HHV6, EBV, parvovirus Nutritional assessments including B12, folate, iron, copper, ceruloplasmin, vitamin D Serum LDH, renal function Work-up for infectious causes Identify marrow hypo/aplasia Bone marrow biopsy and aspirate analysis Peripheral blood analysis, including neutrophil count, proportion of GPI-negative cells by flow for PNH Flow cytometry to evaluate loss of GPI-anchored proteins Type and screen patient for transfusions and notify blood bank that all transfusions need to be irradiated and filtered	
Grading	Management
G1: Nonsevere, <0.5 polymorphonuclear cells x 10 ⁹ /L hypocellular marrow, with marrow cellularity <25%, peripheral platelet count >20,000, reticulocyte count <20,000	Hold ICPi and provide growth factor support and close clinical follow-up, and laboratory evaluation Supportive transfusions as per local guidelines
G2: Severe, hypocellular marrow <25% and two of the following: ANC < 500, peripheral platelet <20,000, and reticulocyte <20,000	Hold ICPi and provide growth factor support and close clinical laboratory evaluations daily Administer ATG + cyclosporine; HLA typing and evaluation for bone marrow transplantation if patient is candidate; all blood products should be irradiated and filtered Supportive care with granulocyte colony-stimulating factor may be added in addition
G3-4: Very severe, ANC >200, platelet count >20,000, reticulocyte count >20,000, plus hypocellular marrow >25%	For G3: Hold ICPi and monitor weekly for improvement; if not resolved, discontinue treatment until AE has reverted to G1 For G4: permanently discontinue ICPi Hematology consult, growth factor support Horse ATG plus cyclosporine If no response, repeat immunosuppression with rabbit ATG plus cyclosporine, cyclophosphamide For refractory patients, consider eltrombopag plus supportive care

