6.8.1. Immune-related Adverse Events

Immune-related AEs are specific to immunotherapies and vary by organ system. Immune-related AEs are important identified risks for bintrafusp alfa.

General management by [NCI-CTCAE v5](#) grading, as per ASCO guidelines, is listed below:

- Grade 1: study treatment should be continued with close monitoring, with the exception of some neurologic, hematologic, and cardiac toxicities.
- Grade 2: study treatment may be suspended for most Grade 2 toxicities, with consideration of resuming when symptoms revert to Grade 1 or less. Corticosteroids may be administered (initial dose of 0.5 to 1 mg/kg/d of prednisone or equivalent).

- Grade 3: study treatment is generally suspended and the high-dose corticosteroids (prednisone 1 to 2 mg/kg/d or methylprednisolone 1 to 2 mg/kg/d) treatment should be initiated. Corticosteroids should be tapered over the course of at least 4 to 6 weeks. Some refractory cases may require infliximab or other immunosuppressive therapy.
- Grade 4: in general, permanent discontinuation of study treatment is recommended, with the exception of endocrinopathies that have been controlled by hormone replacement.

Detailed recommendations for irAE management of specific organ systems as per published guidelines are provided in [Appendix 9](#). These recommendations are in accordance with ASCO Clinical Practice Guidelines in collaboration with NCCN guidelines ([Brahmer, 2018](#)).

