7.1.4. Adverse Drug Reaction Stopping Criteria

Adverse drug reactions are defined in this study as any AEs related to study intervention assessed by the investigator and/or sponsor.

Management guidelines for AEs of Interest (Immune-related AEs, TGF- β -mediated dermatologic AEs, Infusion-related reactions, and treatment-related anemia) as described in Section [6.8](#) supersede the general guidelines below.

Adverse Drug Reactions (ADRs) requiring discontinuation of study treatment include:

- Any Grade 4 ADRs.
- Persistent Grade 3 non-hematologic ADRs that do not recover to Grade 0 or 1 within 6 weeks after dose of treatment Recurrent Grade 3 ADRs (after recovery to Grade 0 or 1) that last more than 72 hours, with optimal medical management, also require discontinuation.
- Any ADR requiring treatment with corticosteroids beyond 12 weeks at doses greater than 10 mg prednisone (or equivalent) per day.

Exceptions to the criteria for discontinuation:

- Fatigue.
- Isolated laboratory values out of normal range that do not have any clinical correlation.
- Endocrinopathies controlled with hormone replacement therapy.
- Tumor flare phenomenon defined as local pain, irritation, or rash localized at sites of known or suspected tumor.
- Keratoacanthomas and/or cSCC (see Section [6.8.2](#)).

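### Appendix 9 aplastic anemia table: every Grade 1 event also meets the Grade 2 definition, so the same counts support two different courses of care

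*Protocol*

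**What the plan says.** Protocol section 6.8.1 points sites to Appendix 9 for organ-level care: "Detailed recommendations for irAE management of specific organ systems as per published guidelines are provided in" that appendix. Section 7.1.4 states that the section 6.8 guidance on adverse events of interest, which includes immune-related events, will "supersede the general guidelines below", meaning the general stopping criteria. The table is therefore in use, not background.

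Table A8, section 8.4 (Aplastic anemia), has three rows:

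- Grade 1: "G1: Nonsevere, <0.5 polymorphonuclear cells x 10"^9/L, hypocellular marrow, "with marrow cellularity <25%, peripheral platelet count >20,000, reticulocyte count <20,000". Care: hold study drug, growth factor, close clinical and laboratory follow-up, transfusions by local guideline.
- Grade 2: "G2: Severe, hypocellular marrow <25% and two of the following: ANC < 500, peripheral platelet <20,000, and reticulocyte <20,000". Care: hold study drug, growth factor, daily laboratory tests, and then "Administer ATG + cyclosporine; HLA typing and evaluation for bone marrow transplantation if patient is candidate".
- Grade 3-4: "G3-4: Very severe, ANC >200, platelet count >20,000, reticulocyte count >20,000, plus hypocellular marrow >25" percent. Care: hold at Grade 3 and stop permanently at Grade 4, hematology consult, horse ATG plus cyclosporine, with further lines if there is no response.

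**The concern.** A grading table that directs treatment should place each set of counts in one row, or say which row wins. Here the nonsevere row sits wholly inside the severe row. The drug action is the same in both (hold), but the remaining care is not: one row is supportive, the other starts intensive immunosuppression and a transplant work-up. A site could follow the protocol and give either.

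The very severe row makes a drafting error more likely. As printed, it asks for counts and marrow cellularity above its cut-offs, where a very severe grade would be expected to ask for values below them. The patients with the worst counts therefore cannot reach the row that carries the hematology consult, the second-line options and permanent discontinuation.

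**Working it through.** The plan states no figure to reproduce. The check is whether the printed definitions are mutually exclusive and ordered.

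**Inputs, all from Table A8, section 8.4.** Unit conversion for Grade 1: 0.5 x 10^9 per liter / 10^6 microliters per liter = 500 per microliter.

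| Criterion | Grade 1 (all four) | Grade 2 (marrow plus two of three counts) | Grade 3-4 (all four) |
|---|---|---|---|
| Neutrophils | <500 | <500 | >200 |
| Platelets | >20,000 | <20,000 | >20,000 |
| Reticulocytes | <20,000 | <20,000 | >20,000 |
| Marrow | <25% | <25% | >25% |

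**Direct logic.** A Grade 1 event has marrow <25%, neutrophils <500 and reticulocytes <20,000. That is the Grade 2 marrow criterion plus two count criteria. The third (platelets <20,000) fails by definition, so exactly two are met. The result is the same whether two of three means at least two or exactly two.

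**Enumeration.** Neutrophils (<200, 200-500, >=500) x platelets (2) x reticulocytes (2) x marrow (2) = 3 x 2 x 2 x 2 = 24 cells.

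- Grade 1: 2 neutrophil levels x 1 x 1 x 1 = 2.
- Grade 2, marrow <25%: neutrophils <500 with at least one other low count, 2 x 3 = 6; neutrophils >=500 with both others low, 1. Total 7.
- Grade 3-4 as printed: 2 x 1 x 1 x 1 = 2.
- Grade 1 and Grade 2 together: 2 of 2. Grade 2 and Grade 3-4 together: 0.

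**Second check.** A grid of 9 x 6 x 5 x 5 = 1,350 numerical combinations, including values at and beside each cut-off, gives 60 Grade 1 points, of which 60 meet Grade 2. Of 212 Grade 2 points, 212 - 60 = 152 are not Grade 1.

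**Sensitivity to one reversed sign in the Grade 1 row.**

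- Neutrophil sign reversed: overlap 0 of 1 cell.
- Reticulocyte sign reversed: overlap 0 of 2 cells.
- Platelet sign reversed: overlap remains (40 of 40 grid points).

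**Grade 3-4 row.** Neutrophils 1,500, platelets 150,000, reticulocytes 60,000 and marrow 40% satisfy it. Neutrophils 100, platelets 5,000, reticulocytes 5,000 and marrow 5% do not, and meet only Grade 2. If all four signs are reversed, the row becomes 1 cell, and that cell also meets Grade 2 (1 of 1).

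**The case against.** The overlap as printed is not disputable, so the case on the other side concerns certainty and weight.

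- **Signs.** The overlap disappears if the Grade 1 neutrophil or reticulocyte sign is wrong, and comparison signs seem to be missing elsewhere in Appendix 9 (for example the prednisone dose for Grade 2 myositis). Those cases suggest omission, not reversal, and nothing in this table points to a misreading. A look at the source file settles it. If a sign is wrong there, that is the error to correct.
- **Source.** The table is adapted from a published guideline that is not in the documents, so the intended cut-offs cannot be stated here. This stands. It is why the correction needs medical confirmation, but it does not excuse overlapping rows in a protocol that adopts the table.
- **Practice.** A clinician whose patient meets a row labelled severe has a reason to use it. Section 6.8.4 also brings in the medical monitor and, for anemia of unknown cause, hematology. These make a poor choice less likely, but none is a tie-break, and the Grade 1 and Grade 2 rows themselves do not require a hematology consult. The worst-grade rule in SAP section 14.1.1.1 governs summary tables, not treatment.
- **Exposure.** Enrollment has stopped, 25 participants were treated, and after the data cut-off care follows local standards (Protocol section 8.2). This limits the weight. Dosing may still continue for up to two years from first dose or confirmed complete response (section 6.10).
- **Grade 3-4 wording.** That row is not milder on every criterion: neutrophils between 200 and 500 satisfy the neutrophil criterion of all three rows. It is milder through platelets, reticulocytes and marrow.

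**Conclusion.** The concern holds. As printed, all Grade 1 events (2 of 2 cells) are also Grade 2, no rule chooses between the rows, and the lowest counts fall outside the very severe row. The consequence is ambiguous patient management for a rare event. The documents give no incidence, and the cell counts describe the table, not patients. The primary response analysis, the CTCAE-graded secondary endpoint and the Grade 3 or higher tables are not affected.

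Assumptions: polymorphonuclear cells are read as the absolute neutrophil count; the Grade 1 criteria are joined by and; counts without units are per microliter; the cell count takes two of three as at least two and ignores values exactly on a cut-off; the signs are as printed.

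**What to change.** Edit the grading cells of Table A8, section 8.4:

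1. Correct Grade 1 so that it excludes Grade 2. Reversing either the neutrophil or the reticulocyte sign does this; which one is a medical question.
2. Check the four inequality directions in the Grade 3-4 row.
3. Add a sentence that the highest row whose definition is met applies. This is needed because a reversed Grade 3-4 row lies inside Grade 2. It is not enough alone: with Grade 1 as printed it would leave that row empty (2 - 2 = 0 cells).
4. Put units on every count.

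With all four Grade 3-4 signs reversed and the highest-row rule in place, Grade 3-4 holds 1 cell, Grade 2 holds 7 - 1 = 6, and Grade 1 holds 1 (neutrophil sign reversed) or 2 (reticulocyte sign reversed), with none shared. The sponsor's medical lead should confirm the cut-offs against the guideline that the appendix adapts.

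The cost is a text edit to three cells and one added sentence. No procedures, visits or data are added.

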8.6 Immune thrombocytopenia	
Definition: An autoimmune disorder characterized by immunologic destruction of otherwise normal platelets	
Diagnostic work-up	History and physical examination (special attention for lymphocyte-depleting therapy, such as fludarabine, ATG, corticosteroids, cytotoxic therapy) Family history of autoimmunity or personal history of autoimmune disease
History of viral illness	
CBC	
Peripheral blood smear, reticulocyte count	
Bone marrow evaluation only if abnormalities in the above test results and further investigation is necessary for a diagnosis	
Patients with newly diagnosed immune thrombocytopenia should undergo testing for HIV, hepatitis C virus, hepatitis B virus, and Helicobacter pylori Direct antigen test should be checked to rule out concurrent Evan syndrome	
Nutritional evaluation	
Bone marrow evaluation if other cell lines affected and concern for aplastic anemia	
Grading	Management
G1: Platelet count <100/ μ L G2: Platelet count <75/ μ L	Continue ICPi with close clinical follow-up and laboratory evaluation Hold ICPi but monitor for improvement; if not resolved, interrupt treatment until AE has reverted to G1 Administer prednisone 1 mg/kg/d (dosage range, 0.5-2 mg/kg/d) orally for 2-4 weeks after which time this medication should be tapered over 4-6 weeks to the lowest effective dose IVIG may be used in conjunction with corticosteroids if a more-rapid increase in platelet count is required.
G3: Platelet count <50/ μ L	Hold ICPi but monitor for improvement; if not resolved, interrupt treatment until AE has reverted to G1
G4: Platelet count <25/ μ L	Hematology consult Prednisone 1-2 mg/kg/d (oral or IV depending on symptoms) If worsening or no improvement, 1-2 mg/kg/d prednisone equivalents and permanently discontinue treatment IVIG used with corticosteroids when a more-rapid increase in platelet count is required

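### Protocol Appendix 9, Table A8 misprints two irAE grading rules: the aplastic anemia G3-4 signs contradict G2, and the immune thrombocytopenia cut-offs are 1000-fold too low

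*Protocol*

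**What the plan says.** Protocol Section 6.8.1 sets general rules by CTCAE v5 grade, then sends sites to Appendix 9 for organ-specific advice. Section 6.8.5.1 names Table A8 directly for a rapid fall in hemoglobin. Section 7.1.4 lets the Section 6.8 guidance on immune-related events override its own list of stopping reasons, which includes any Grade 4 adverse drug reaction.

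Table A8, 8.4 Aplastic anemia, has three criteria rows:

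- G1: "Nonsevere, <0.5 polymorphonuclear cells x 10" to the ninth per liter, "with marrow cellularity <25%, peripheral platelet count >20,000, reticulocyte count <20,000".
- G2: "Severe, hypocellular marrow <25% and two of the following: ANC < 500, peripheral platelet <20,000, and reticulocyte <20,000". Treatment is held, with daily laboratory checks, ATG plus cyclosporine, and "HLA typing and evaluation for bone marrow transplantation if patient is candidate".
- G3-4: "Very severe, ANC >200, platelet count >20,000, reticulocyte count >20,000, plus hypocellular marrow >25" percent. The actions are "For G3: Hold ICPi and monitor weekly for improvement; if not resolved, discontinue treatment until AE has reverted to G1" and "For G4: permanently discontinue ICPi Hematology consult, growth factor support".

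Table A8, 8.6 Immune thrombocytopenia, starts at "G1: Platelet count <100" per microliter for G1 and continues with 75, 50 and 25 per microliter for G2, G3 and G4. Treatment continues at G1. At G2 and G3 it is held until the event returns to G1.

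**The concern.** A worse grade of marrow failure cannot require higher counts than a milder one, yet the G3-4 row does so on all four measures. A platelet grade that begins below 100 per microliter also cannot belong to a protocol whose entry minimum is 100 x 10^9/L.

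Both rows decide whether dosing is continued, held or stopped for good. A site that applied 8.4 literally would not find the row carrying the permanent-discontinuation instruction for its sickest patient. A site that applied 8.6 literally would find no row for a clinically important platelet fall.

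**Working it through.** No sample size or error rate is involved. The check sets the rows against each other and converts units.

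**Aplastic anemia, G2 against G3-4.** Take ANC 100, platelets 10,000 and reticulocytes 10,000 (all per microliter) and marrow 20%.

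| Measure | Value | G2 as printed | G3-4 as printed | G3-4 with signs reversed |
|---|---|---|---|---|
| Marrow | 20% | <25%: yes | >25%: no | <25%: yes |
| ANC | 100 | <500: yes | >200: no | <200: yes |
| Platelets | 10,000 | <20,000: yes | >20,000: no | <20,000: yes |
| Reticulocytes | 10,000 | <20,000: yes | >20,000: no | <20,000: yes |

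The case meets G2 (marrow plus three of three, where two are needed), 0 of 4 printed G3-4 conditions, and 4 of 4 reversed ones. Because marrow cannot be both below and above 25%, no case can meet both printed rows. In the other direction, ANC 4,000, platelets 250,000, reticulocytes 60,000 and marrow 40% satisfies all four printed G3-4 conditions.

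Reversing the signs restores the order: marrow <25% with all three counts low always meets G2, so G3-4 becomes a stricter subset. With ANC 300 and the other three values unchanged, 3 of 4 reversed conditions hold and the case stays G2. The limit of 200 then does the separating.

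**Aplastic anemia, G1 against G2.** 0.5 x 10^9/L = 0.5 x 10^9 / 10^6 = 500 per microliter, the same limit as in G2. Printed G1 therefore requires marrow <25%, ANC <500 and reticulocytes <20,000, which already gives G2 its marrow condition and two of its three counts. Example: ANC 400, platelets 50,000, reticulocytes 15,000 and marrow 20% meets both rows. If the G1 ANC sign were '>' instead, G1 would supply only the reticulocyte count (its platelets are above 20,000), and the overlap would vanish.

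**Enumeration.** The grid is ANC 0 to 1,000 by 50, platelets 0 to 100,000 by 5,000, reticulocytes 0 to 80,000 by 5,000 and marrow 0 to 60% by 5, so 21 x 21 x 17 x 13 = 97,461 points.

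- Printed G1 holds at 10 x 16 x 4 x 5 = 3,200 points, all of which meet G2.
- Reversed G3-4 holds at 4 x 4 x 4 x 5 = 320 points; all meet G2 and none meets printed G3-4.

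**Immune thrombocytopenia.** Protocol Section 5.1, criterion 7, sets the platelet minimum at 100 x 10^9/L = 100 x 10^9 / 10^6 = 100,000 per microliter. Against the printed G1 limit, 100,000 / 100 = 1000.

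| Grade | Printed, per microliter | Same number x 10^9/L, per microliter |
|---|---|---|
| G1 | <100 | <100,000 |
| G2 | <75 | <75,000 |
| G3 | <50 | <50,000 |
| G4 | <25 | <25,000 |

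Section 8.4 of the same table treats 20,000 as a low platelet count, which is 20,000 / 25 = 800 times the printed G4 limit in 8.6. A confirmed case at 60,000 lies above every printed cut-off. With the unit restored it falls between 50,000 and 75,000, which is G2 (hold). The band for returning to G1 is printed as 75 to <100 instead of 75,000 to <100,000.

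**The case against.** The strongest reply concerns consequence. Appendix 9 offers recommendations based on expert consensus, and the investigator may stop treatment for safety at any time. A very severe aplastic anemia read as G2 still has treatment held, with daily laboratory checks against weekly in the G3 action, and the G2 row gives no rule for resuming. Section 6.8.1 recommends permanent discontinuation in general at Grade 4. For platelets, the eligibility table shows the intended unit. Enrollment has closed with 25 treated, and after the data cut-off care follows local practice (Section 8.2). All of this stands and keeps the point small. It does not make the rows right: sites are sent to them, Section 7.1.4 gives them precedence, and under Section 6.10 continued dosing after the cut-off still requires that no protocol discontinuation criterion is met.

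Three stronger readings are tempting but unsupported.

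- A reader might infer that 8.4 is also defective because G3 (hold) and G4 (discontinue) share one row. That is the appendix's usual layout; inflammatory arthritis, myositis, polymyalgia-like syndrome, aseptic meningitis and encephalitis have it too.
- A reader might treat the G1 overlap as a third established error. It holds on the printed text but rests on a single ANC sign, so it calls for a check against the source.
- A reader might want an interim instruction to discontinue at CTCAE Grade 4. Section 6.8.1 already says this in general. The documents print no CTCAE criteria for aplastic anemia, so its fit with Table A8 cannot be verified.

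**Conclusion.** The point stands and should be fixed, but its reach is narrow. Two rules in Table A8 are wrong as printed: all four signs in the aplastic anemia G3-4 row, and the unit of all four immune thrombocytopenia cut-offs, by a factor of 1000.

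The sign error follows from the G2 and G3-4 rows alone. The factor of 1000 is inferred from the protocol's platelet scale and the limits in 8.4. Confidence that both are wrong is high. Confidence in the exact replacement values is moderate, since they need the source guideline. A fault in converting the PDF to text cannot be fully excluded, but four signs and four units failing in the same way make it unlikely.

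A reader might infer that trial results are affected. They are not. The primary endpoint is RECIST response, and SAP 14.1.1.1 and 14.3.1 grade adverse events and laboratory values by CTCAE v5. The effect is limited to the management of rare hematologic immune-related events in participants still being dosed, whose number the documents do not state.

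**What to change.** Send a short erratum to sites with participants on treatment:

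1. In Table A8, 8.4, change the four G3-4 signs to '<': ANC <200, platelets <20,000, reticulocytes <20,000, marrow <25%.
2. In Table A8, 8.6, change the cut-offs to 100, 75, 50 and 25 x 10^9/L.
3. At the same time, check the sign of the G1 ANC limit in 8.4, because G1 as printed always also meets G2.

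Before it goes out, the sponsor's medical team should confirm the values against the ASCO guideline that Appendix 9 names as its source. The cost is one letter, with no change to the primary endpoint, the adverse event analysis or the database.
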